- Timeline Follow-Back (TLFB) (Sobell and Sobell, 1992; 2000) assesses self-reported alcohol and other drug use (frequency, quantity) using calendars and memory aids to enhance recall. We will not be able to provide printed calendars; however, the participant will be encouraged to use their phone or tablet device to view a calendar app to help enhance their recall of past substance use. The TLFB has good psychometric properties, including test-retest reliability with multiple populations, and content, criterion, and construct validity across multiple related measures. Additional questions will assess intensity and number of days of urges/cravings for opioids and other substances, and HIV risk as a result of IV drug use and sharing of needles/works. Per the recommendation of the NIH, staff who are blinded to the randomization assignment of participants should complete the TLFB. Penn State research staff will complete the TLFB during baseline because it will be completed before randomization occurs. Columbia research staff will be completing the TLFB via phone/WebEx session with all subjects beginning with the 4-week follow-up visit. During the follow-up visits, Penn State research staff will complete all research tasks with the participants and help facilitate the TLFB with the Columbia team by:
 - Transferring the participants to the Columbia team by phone, text or email;
 - Providing a phone number or meeting room link so participants could reach out to the Columbia team directly; and/or
 - Providing the Columbia team with the participant's contact information (at the participant's request).
 - The research tasks with the Columbia team will occur through the participant's phone or an office phone via WebEx. Columbia University requires the use of WebEx for research outreach to participants.
- Coping Strategies Scale (CSS) (Litt et al., 2003) is a 23-item, self-report measure (originally adapted from the Processes of Change (Proschaska et al., 1998)), assessing change processes, coping skills, and problem-solving related to urges to use substances. It has good reliability across samples ($\alpha=.83$ to $.87$). Two versions with only slight differences in directions will be administered. At intake, the directions will ask subjects to think about the last three months

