when answering the questions. For all follow-up research appointments, the directions will ask the subject to think about their coping strategies used since the last research appointment. Question/prompt items remain the same between the two versions.

- PROMIS is a well validated and widely used scale that measures the quality of social and occupational functioning.
- Social Connectedness Scale (SCS) (Lee and Robbins 1995; 1998) is a 20 item, 6-point scale, self-report assessing psychological belonging or interpersonal closeness with good reliability ($\alpha=.91$).
- Patient Health Questionnaire (PHQ) (Spitzer et al., 1999) was developed for use in primary health settings and screens for DSM psychiatric diagnosis of major depression and generalized anxiety at baseline.
- The Kessler 10 (K10) (Kessler et al., 2003) is a brief, 10-item self-report measure of general psychiatric distress will be collected at baseline and follow up points to address change in psychiatric symptoms over time. K10 has good reliability and is used in World Health Organization mental health surveys in 30 countries.
- HIV Risk from the Sexual Experiences and Risk Behavior Assessment Schedule (SERBAS): A summary item from the Sexual Experiences and Risk Behavior Assessment Schedule (SERBAS), used as primary outcome in large HIV risk reductions studies (Tross et al., 2010), elicits the number of episodes of occasions of vaginal or anal intercourse without a condom over the last 90 days using time-line follow back cues for recall.
- Time Line Follow-Back (see above) will query intravenous drug use, and episodes of sharing needles.
- Columbia Suicide Severity Rating Scale (C-SSRS) (Posner et al., 2008):_ The C-SSRS will be administered only to subjects who have endorsed suicidal ideation (SI) per the Patient Health Questionnaire (PHQ). There is one item on the PHQ that assesses self-reported SI using a Likert scale of 0-3 (0 = not at all; 3= nearly every day). A score of 1 or higher is considered an SI endorsement, which will warrant administration of the C-SSRS. Should the C-SSRS results indicate an SI presence/plan, a Hub PPI provider (physician or nurse practitioner) will take over the evaluating situation and follow PPI's SI policy.

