- Intervention Acceptability/Feedback Form (IAFF) is a 7-item self-report measure comprised of indicators of treatment acceptability on 10-point scales: interesting, useful, new information, easy to understand, satisfaction, relevance to life, and likability. This will only be administered to patients who have been assigned to TAU + reSET-O.
- TAU Tracking Form (TTF) –completed by research staff in order to capture services received in TAU per week over past 4 weeks, including modality and frequency. Research staff will verify the information with the patient for accuracy.
- reSET-O Implementation and Adherence: For participants who have been assigned to TAU +reSET-O, we will collect data from the reSET-O data system and dashboard for each patient on utilization of reSET-O features (how many and which therapy lessons are completed, incentives earned, use of the communication features).
- Weiner Intervention Appropriateness, Acceptability and Feasibility Survey: This survey will be completed by providers who are engaged with the app. This survey evaluates acceptability,

appropriateness, and feasibility of intervention implementation using a 5-point Likert scale (1=lowest score; 5=highest score).

In cases where the Timeline Follow-Back assessment cannot be completed (patient cannot access the Columbia team's WebEx room, patient must leave the research visit before completing), Penn State research staff will pull data from the Demographic Questionnaire Form that the patient completes during their intake process (attached to this modification). This questionnaire is also administered by Penn State research staff as part of routine intake. This data query is necessary because of the time sensitive nature of self-reported alcohol and drug use data (i.e. asking about a patient's alcohol and drug use in the last 30 days).

- HITS (Hurt-Insult-Threaten-Scream Screening Tool): This assessment screens for domestic violence in participants who have a romantic partner. It will be used at both the baseline and endpoint visits.
- BARC-10 (Brief Assessment of Recovery Capital): This is a 10-item measure that assesses the level of personal, social, physical and professional resources that someone has available.
- PCL-C (PTSD Checklist – Civilian Version): A self-report rating scale for symptoms of PTSD over the past 1 month.

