7.4.5 Blinding of the Test Article

Per the recommendation of NIH, the TLFB should be completed by staff blinded to the randomized assignment of the participants. Penn State research staff will complete the TLFB with participants because this occurs before randomization. All TLFB conducted after the

baseline visit will be conducted by an external research team member who is blinded to the randomization assignments. Upon completion of the TLFB, the external staff member will transmit files to the Penn State research team via Accellion/ Kite Drive for e-storage of the document (on the Hershey Medical Network server, accessible through role-based security only), and entry into REDcap. No PHI is collected or exchanged during the TLFB process.

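### The fallback for a missed Timeline Follow-Back points to intake-form data, which predate the four-week outcome window at weeks 8, 12 and 24

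*Combined protocol and SAP*

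**What the plan says.** The fallback stands in Section 7.2.1, in the list of measures. If the TLFB cannot be completed, "Penn State research staff will pull data from the Demographic Questionnaire Form that the patient completes during their intake process". Two triggers are named. The first is "patient cannot access the Columbia team's WebEx room"; the second is that the patient has to leave the visit early. The reason given is that self-reported use is time-sensitive, described as "asking about a patient's alcohol and drug use in the last 30 days".

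On who conducts the TLFB, Section 7.2.1 says "Columbia research staff will be completing the TLFB via phone/WebEx session with all subjects beginning with the 4-week follow-up visit". Section 7.4.5 agrees: every TLFB after the "baseline visit will be conducted by an external research team member who is blinded to the randomization assignments". Penn State staff do the baseline TLFB, before randomization.

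Section 7.2.2 repeats the listed procedures and measures at weeks 4, 8, 12 and 24, counted from the baseline questionnaires and randomization. Section 8.3 defines days of opioid use and days of other drug or alcohol use over the last four weeks, as longitudinal secondary outcomes. Apart from urine-confirmed abstinence, which has its own rule, it treats missing secondary data as missing at random and adds sensitivity analyses that impute the missing data. It does not mention the intake-form fallback.

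**The concern.** The rule sits under the intake and baseline visit, but its first trigger belongs to follow-up. Taken literally, a TLFB missed at week 12 sends staff to a form filled in before the patient was randomized. Those answers describe use around treatment entry, not use in the four weeks before the visit.

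If such values went into the follow-up field, the two days-of-use outcomes would contain pre-randomization measurements labelled as post-randomization ones. The values would no longer be recorded as missing, so the missing-at-random treatment in Section 8.3 would not apply to them and, unless they were flagged, the sensitivity imputations would pass over them too. The direction of any bias would depend on how often this happened in each arm and in which patients; the documents give neither.

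**Working it through.** The plan states no figure for this timing, so there is none to reproduce. The check has two steps.

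**1. Does the rule reach follow-up visits?** The WebEx trigger needs a Columbia TLFB session. Sections 7.2.1 and 7.4.5 place Columbia sessions only after baseline. So that trigger cannot occur at baseline, and a baseline-only reading would leave it without meaning. The early-departure trigger can occur at any visit.

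**2. Can intake recall overlap the outcome window?** Inputs:

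- R, days from intake to randomization: 0 to 42, from the consent timing in Section 5.2.1. Sections 4.1 and 7.2.1 give a narrower appointment interval of 7 to 21 days.
- V, days from randomization to visit, from the windows in Section 7.2.2: week 4 ± 2 weeks = 14 to 42; week 8 ± 2 = 42 to 70; week 12 ± 2 = 70 to 98; week 24 (+2/−4) = 140 to 182.
- Outcome look-back: four weeks = 28 days, from Section 8.3.
- Assumptions: the form is completed on the intake day (day 0), its recall ends that day, and randomization falls on the consent day. Later randomization only lengthens the gap.

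The outcome window opens on day R + V − 28 after intake, and intake recall ends on day 0. So

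gap = R + V − 28, where a negative value is an overlap.

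| Visit | Smallest gap, R = 0 | Largest gap, R = 42 | Range with R = 7 to 21 |
|---|---|---|---|
| Week 4 | 0 + 14 − 28 = −14 | 42 + 42 − 28 = 56 | −7 to 35 |
| Week 8 | 0 + 42 − 28 = 14 | 42 + 70 − 28 = 84 | 21 to 63 |
| Week 12 | 0 + 70 − 28 = 42 | 42 + 98 − 28 = 112 | 49 to 91 |
| Week 24 | 0 + 140 − 28 = 112 | 42 + 182 − 28 = 196 | 119 to 175 |

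No permitted combination gives any overlap at weeks 8, 12 or 24. At week 4 an overlap needs an early visit and a short lag from intake; the most it can be is 14 of 28 days. The result does not depend on which lag applies. If the intake process is taken to mean the baseline visit itself, R = 0 and the smallest gaps still stand. The length of the form's recall period does not enter the gap, since only its end point matters.

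**The case against.** The best reply is that this is loose drafting. The form is an attachment that the reviewed documents do not include. The text says it is also given at routine intake, and that word could hint at other occasions. Section 7.2.2 repeats the listed measures at each follow-up. The stated reason, time-sensitive recall, fits a form filled in on the day, or a missed baseline TLFB shortly after intake, much better than data that are months old. Section 8.3, which governs the analysis, never adopts the fallback; read alone, it leaves a missed TLFB missing.

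Much of this stands. No passage says that the form is given again at follow-up, so the literal reading remains, but the intent is open. Several stronger readings that a reader might infer are not supported:

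- *That the trial will analyse intake values as follow-up outcomes.* The documents say that data are pulled, not where they are entered.
- *That craving, needle sharing or urine-confirmed abstinence are also affected.* The fallback speaks only of alcohol and drug use, nothing shows that the form carries the other items, and abstinence has its own missing-data rule.
- *That the form and the outcome have different recall lengths.* The 30-day remark describes self-reported use data in general and is not clearly the form's own period.
- *That the bias can be sized.* The documents give no rate of missed TLFBs, and no mean or spread for days of use.
- *That the intake data are unblinded.* They precede randomization; the fault is timing.

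What survives is narrower but real: a written instruction to staff that, followed as a substitute at follow-up, conflicts with Section 8.3.

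**Conclusion.** The concern holds as a conflict between a data-collection rule and the analysis plan, and it should be fixed. The firm result is the time mismatch tabulated above: intake recall misses the outcome window entirely at weeks 8, 12 and 24, by at least 14, 42 and 112 days, and covers at most half of it at week 4. This rests on the form being completed once, at intake, as Section 7.2.1 states.

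The consequence is conditional. Only if pulled values are used as follow-up values are the two days-of-use outcomes misstated and the missing-data rule bypassed. Those outcomes are secondary. The primary retention outcome and the sample size are not touched.

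**What to change.** Reconcile Sections 7.2.1 and 8.3 by stating in both that:

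- intake-form data may stand in only for a missed baseline TLFB and are never entered as a follow-up value;
- a follow-up TLFB not completed within the existing visit window is treated as missing under Section 8.3;
- any intake values pulled at a follow-up visit are flagged in REDCap and excluded from the outcome analyses.

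If the sponsor meant a form completed at the follow-up visit itself, name that form, give it a last-four-weeks look-back, flag its values, and note that Penn State staff administering it would not be the blinded assessor that Section 7.4.5 calls for.

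The cost is a few sentences and one flag variable. The downside is slightly more missing follow-up self-report data. Repeat attempts by the blinded team within the window can recover some of it, but not all: Section 7.2.1 notes that "Columbia University requires the use of WebEx for research outreach to participants", so a patient who cannot use that route once may fail again.

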7.3 Duration of Participation

All participants are asked to participate in 5 remote or in-person research visits over 24 weeks as listed above, as well as participate in two phone check-ins at week 16 and week 20. The baseline visit will take about 1 to 1.5 hours for subjects assigned to reSET-O +TAU, and 45 minutes to 1hour for subjects assigned to TAU only. For reSET-O + TAU subjects, follow-up appointments will last 30 to 45 minutes, with the exception of the visit that accounts for the addition of a qualitative interview (weeks 4, 8 or 12), which will last approximately 50 to 65 minutes to account for the qualitative interview. For subjects who have been assigned to TAU only, follow-up visits will take 20-30 minutes to complete.

7.4 Test Article(s) (Study Drug(s) and/or Study Device(s))

7.4.1 Description

reSET-O: Mobile App Delivering Cognitive-Behavioral Intervention to Enhance Implementation of MAT

reSET-O is the commercially available version (Pear Therapeutics, Inc.) of the Therapeutic Education System (TES) originally developed by Bickel, Marsch and colleagues (2008). It was recently approved by the FDA as the first digital therapeutic adjunct for the treatment of substance use disorders. Pear Therapeutics has agreed to provide reSET-O for this proposed project without cost and to collaborate on any modifications that arise during the R21 phase. reSET-O (TES) combines two empirically supported treatment approaches, Community Reinforcement Approach (CRA) and Contingency Management (CM), translating them onto a computer-interactive learning environment, delivered by smartphone or tablet, without the direct involvement of a human therapist. CRA is based on the model that substance use disorders develop when drug reinforcers grow in salience and displace an individual's normal healthy sources of reinforcement, such as friends, family, employment, and recreation. CRA teaches patients cognitive-behavioral coping skills to resist drug use and to address factors such as craving, depression and other mood problems, and relationship issues that are associated with risk of relapse, in order to rebuild their lives and relationships without drugs. CM provides concrete monetary rewards (e-giftcards) contingent on performance of one or several key target behaviors, such as urine-confirmed abstinence from drugs or attendance at treatment appointments. CRA and CM are both highly researched therapeutic interventions for substance use disorders with broad empirical support individually (Hunt & Azrin 1973; Budney & Higgins 1998; Miller & Meyers 1998; Stitzer & Petry 2006). When delivered together, CRA and CM have

been shown to contribute uniquely to outcomes, suggesting complementary therapeutic elements that enhance overall treatment effectiveness (Roozen et al., 2004; Higgins et al., 1994; 2003).

MAT treatment (treatment as usual) when combined with counseling has a decent success rate at greater than 50% patient retention over a 6-month period. Patients retained in MAT treatment typically experience substantial improvement in their opioid use, while those who discontinue MAT typically relapse to opioid use. Therefore it is important to try to improve the rate of retention in treatment, which is why the reSET-O intervention is proposed. Patients enrolling in the study will have been prescribed their appropriate MAT as their standard of care and is not part of the research study.

7.4.2 Treatment Regimen

reSET-O is delivered as a mobile app and can be downloaded to and used by a smart phone or tablet. Buprenorphine-naloxone and buprenorphine dosing ranges from 2-24mg/day, is administered sublingually, and in combination with counseling. Methadone dosing ranges from 60-250mg/day, is administered orally, and in combination with counseling. For buprenorphine-naloxone, buprenorphine, and methadone, initial doses are started low to avoid precipitated withdrawal and titrated upwards to achieve relief of withdrawal symptoms and avoid cravings.

7.4.3 Method for Assigning Subject to Treatment Groups

Subjects will be randomly assigned to TAU alone or TAU + reset-O, but stratified by MAT into three arms: methadone, buprenorphine initiated at the Hub and buprenorphine initiated as a bridge appointment with continuation of treatment at the spoke.

Randomization will be determined through a web-based data management system. The stratification data will be entered and the data management system will conduct the randomization and communicate back with the treatment assignment within the same web-based interface.

7.4.4 Subject Compliance Monitoring

The Contingency Management system developed in TES, and adapted in reSET-O, utilizes the “prize bowl” method developed by Petry to deliver contingency management at lower cost (cost of the incentives) to make it more feasible for community-based treatment. When a target behavior is performed (completing a therapy lesson, attending a clinic appointment), the patient earns a “draw”, where some draws yield motivational messages, some are low cost prizes, with the occasional higher value prize. The program keeps track of the draws earned and prizes, so that, again, burden on clinical to organize the CM intervention is minimized. Completion of therapy lessons automatically earns draws.

In order to further support buprenorphine adherence, reSET-O contains communication features, where the patient receives a daily prompt to take their buprenorphine dose, and can record taking each dose, as well as any drug use or craving. This information, along with information on which therapy lessons a patient has completed, is summarized on a dashboard for each patient available that is available on line to the prescribing physician and other clinicians (research coordinator/research assistant in the study proposed here) to help track progress and stimulate discussion between patients and their clinicians.

7.4.5 Blinding of the Test Article

Per the recommendation of NIH, the TLFB should be completed by staff blinded to the randomized assignment of the participants. Penn State research staff will complete the TLFB with participants because this occurs before randomization. All TLFB conducted after the

baseline visit will be conducted by an external research team member who is blinded to the randomization assignments. Upon completion of the TLFB, the external staff member will transmit files to the Penn State research team via Accellion/ Kite Drive for e-storage of the document (on the Hershey Medical Network server, accessible through role-based security only), and entry into REDcap. No PHI is collected or exchanged during the TLFB process.

7.4.6 Receiving, Storage, Dispensing and Return

7.4.6.1 Receipt of Test Article

Participating patients assigned to TAU + reSET-O will download the free reSET-O app to their own smartphones, but for those who do not own a smartphone, a smartphone will be provided for the duration of the trial.

7.4.6.2 Storage

Approximately 75 inexpensive smartphones or tablets will be maintained by study personnel.

7.4.6.3 Preparation and Dispensing

N/A

7.4.6.4 Return or Destruction of the Test Article

N/A

7.4.6.5 Prior and Concomitant Therapy

N/A

8.0 Subject Numbers and Statistical Plan

8.1 Number of Subjects

We will recruit and enroll 200 patients with OUD within the Penn State Hub and Spoke System (Pennsylvania Coordinated Medication Assisted Treatment (PACMAT), for this RCT.

Due to the possibility of turnover and new hires, we expect approximately 12-15 providers to engage with and provide feedback on the app. Any new hires will not engage with the app until CITI and HIPAA training is completed and a modification reflecting a team member change has been approved by this IRB. The team member form will be reviewed on a bi-monthly basis and updated as appropriate with any changes, and the IRB will be notified as soon as possible regarding these updates.

Research subjects will not be assigned to any newly hired provider until the said provider has completed the appropriate CITI and HIPAA training, and has officially been added to the study team and approved through the Penn State IRB.

8.2 Sample size determination

Previous studies of MAT treatment of OUD indicate substantial drop out rates--typically in the 40% to 50% range still retained in treatment at 24 weeks. Assuming 40% retention in the TAU treatment group, a sample size of 100 patients per treatment group (total N = 200) is selected to ensure sufficient power of 80% with a two-sided level of significance of 5% to be able to detect a difference of at least 19.7% between the TAU vs reSET-O + TAU treatment groups (i.e., 40% retained in TAU vs 59.7% retained in reSET-O + TAU). This difference of 19.7% is equivalent to an odds-ratio of 2.22 and would be clinically meaningful.

